4.4.2.4 Proportion of patients with rejection episodes

Proportion of patients with presumed or biopsy-proven AMR episodes (classified according to Banff 2017 or later) and proportion of patients with biopsy-proven rejection episodes, (other than AMR episodes) within 3 years after start of treatment in feeder trial will be listed and summarised by treatment group.

4.4.2.5 DSA level at 1, 2, and 3 years after start of treatment in feeder trial

DSA levels (measured using SAB-HLA assay) at 1, 2 and 3 years after start of treatment in the feeder trial will be summarized, listed, and presented graphically. The individual plots, will include sum of DSA as a separate line. Mean plots will display the mean of "sum of DSA".

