- Proportions of subjects with presumed or biopsy proven AMR episodes (classified according to Banff 2017 or later version) within 3 years after start of treatment in feeder trial
- Proportion of subjects with presumed or biopsy-proven rejection episodes, (other than AMR episodes) classified according to Banff 2017 or later version) up to 3 years after start of treatment in feeder trial
- DSA levels at 1, 2, and 3 years after start of treatment in feeder trial
- Anti-imlifidase IgG at 1, 2, and 3 years after start of treatment in feeder trial

Methodology

This is an observational 3-year follow up trial. The trial will primarily evaluate kidney graft survival in subjects with active or chronic active AMR treated with imlifidase or plasma exchange. Subjects that have participated in trial 16-HMedIdeS-12 (called the feeder trial) will be asked to participate. The subjects will attend three follow up visits 1, 2, and 3 years after start of treatment in the feeder trial.

Trial Procedures/Assessments

At all visits, graft survival and information about graft rejection episodes will be assessed. Blood samples for graft function (creatinine and eGFR), and analysis of DSA and ADA will be collected as well as a urine sample for albumin/creatinine ratio. Information about patient survival and comorbidity (infections, malignancy, diabetes mellitus, cardiovascular events and comorbidity leading to worsening of kidney function) will be recorded.

Number of subjects

Up to 30 subjects will be included.

Diagnosis and main criteria for inclusion/exclusion

Inclusion criteria:

- Signed Informed Consent obtained before any trial-related procedures
- Willingness and ability to comply with the protocol
- Previous treatment with imlfidase or plasma exchange in trial 16-HMedIdeS-12

Exclusion criteria:

- Inability by the judgement of the investigator to participate in the trial for any other reason

Medicinal Product(s)

Not applicable

Duration of treatment

Each subject will be followed up 1, 2, and 3 years after start of treatment in feeder trial.

Statistical methods

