2.2.2 Secondary Endpoints

Secondary endpoints of this trial are:

- Overall graft survival evaluated at Year 1 and 2
- Patient survival, evaluated at 3 years after start of treatment in feeder trial
- Kidney function, as evaluated by eGFR, S/P-creatinine and albumin/creatinine ratio in urine at 1, 2, and 3 years after start of treatment in feeder trial
- Proportions of subjects with presumed or biopsy proven AMR episodes (classified according to Banff 2017 or later version) within 3 years after start of treatment in feeder trial
- Proportion of subjects with presumed or biopsy-proven rejection episodes, (other than AMR episodes) (classified according to Banff 2017 or later version) up to 3 years after start of treatment in feeder trial
- DSA levels at 1, 2, and 3 years after start of treatment in feeder trial
- Anti-imlifidase IgG at 1, 2, and 3 years after start of treatment in feeder trial

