12.4.4 Proportion of subjects with rejection episodes

Proportion of subjects with presumed or biopsy-proven AMR episodes (classified according to Banff 2017 or later) and proportion of subjects with biopsy-proven rejection episodes, (other than AMR episodes) within 3 years after start of treatment in feeder trial will be listed and summarised by treatment group.

12.4.5 DSA level at 1, 2, and 3 years after start of treatment in feeder trial

DSA levels (measured using SAB-HLA assay) 1, 2 and 3 years after start of treatment in feeder trial will be summarized, listed, and presented graphically.

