1.1.2 Endpoints

The primary endpoint of this trial is:

- To evaluate the overall graft survival at Year 3.

Secondary endpoints of this trial are:

- Overall graft survival evaluated at Year 1 and 2.
- Patient survival, evaluated at 3 years after start of treatment in feeder trial.
- Kidney function, as evaluated by estimated Glomerular Filtration Rate (eGFR), S/P-creatinine and albumin/creatinine ratio in urine at 1, 2, and 3 years after start of treatment in feeder trial.
- Proportions of patients with presumed or biopsy proven AMR episodes (classified according to Banff 2017 or later version) within 3 years after start of treatment in feeder trial.
- Proportion of patients with presumed or biopsy-proven rejection episodes, (other than AMR episodes) (classified according to Banff 2017 or later version) up to 3 years after start of treatment in feeder trial.

- DSA levels at 1, 2, and 3 years after start of treatment in feeder trial.
- Anti-imlifidase IgG at 1, 2, and 3 years after start of treatment in feeder trial.

[figure not shown]
2 Study design

The study is an observational 3-year follow up trial after the 16-HMedIdeS-12 study. The purpose of this trial is to investigate the long-term outcomes of imlifidase or plasma exchange treatment on active or chronic active AMR in kidney transplant recipients. The long-term outcomes are evaluated by considering the overall graft survival, patient survival, kidney function, DSA levels, AMR episodes, and anti-imlifidase IgG.

A maximum of 30 patients can be included depending on patients' willingness to participate in the trial after the 16-HMedIdeS-12 study.

The flow of the study is displayed in Figure 1 below.

Figure 1.

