4.5.1.1 Adverse Event

An AE is the development of an undesirable medical condition or the deterioration of a pre-existing medical condition following or during exposure to a pharmaceutical product or trial procedure. No IMP will be administered in this trial and only AEs that the investigator judges as related to IMP administered in the feeder trial, and adverse events caused by a procedure in the protocol (such as blood sampling) will be captured and reported in this trial.

An AE overview summary table will be prepared including the number of patients reporting an AE, the percentage of patients (%) with an AE, and the number of events (E) reported for the following categories:

- All AEs
- AEs – by System Organ Class (SOC) and Preferred Term (PT)
- AEs – by causality

- AEs – by severity
- Serious AEs (SAEs)
- Serious AEs (SAEs) – by causality
- Serious AEs (SAEs) – leading to death
- Serious AEs (SAEs) – leading to withdrawal

Data listings will be provided for:

- All AEs sorted by patient number
- All AEs sorted by MedDRA SOC and PT
- SAEs

5 Interim analyses

No interim analyses were performed.

6 Deviations from protocol analysis

The study was terminated prematurely in January 2023 due to an internal decision that will allow Hansa to focus on prioritised projects and allocate resources in the way the company deems most effective according to its strategic priorities.

7 Quality control

The quality control of the data will be performed as follows:

- By Data Management for all CRF data following the data validation plan
- By Statistics and Programming for all data received

The QC depends on the process below, but it will follow █ SOP 703 Single Use Programs:

SDTM data sets will be generated by programs in the Statistical analysis system (SAS) by reading in lab data and export data to SDTM formats following the SDTM specifications. The QC will include:

- Independent Code review
- CRF annotation review vs SDTM content
- Run of Pinnacle verification
- QC of CRF input vs output in SDTM on a sample of data
- Format and fonts in annotated CRF

ADaM data sets will be based on the SDTM data sets. The programming of the ADaM datasets will be performed in SAS and QC of the programs will include

- Independent code review
- Run of Pinnacle verification
- QC of SDTM input data vs output in ADaM or listings

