9.1 Tables

Table 14.1.1 Patient disposition, including reason for discontinuation (All screened patients).

Table 14.1.2 Protocol Deviations (FAS).

Table 14.1.3 Demography and body measurements (FAS).

Table 14.1.4 Medical and surgical history (FAS).

Table 14.1.5 Concomitant medication (FAS).

Table 14.1.6 Previous transplant kidney history (FAS).

Table 14.2.1 MFI levels for DSA – by time point (FAS).

Table 14.2.2 Kidney function (based on S/P-creatinine analysis) (FAS).

Table 14.2.3 Proportion of patients with absence of graft loss at 1 year, 2 years and 3 years (FAS)

Table 14.2.4 Proportions of patients with presumed or biopsy proven AMR episodes (FAS).

Table 14.2.5 Proportion of patients with presumed or biopsy-proven rejection episodes, (other than AMR episodes) (FAS).

Table 14.2.6 Total IgG – by timepoint (FAS).

Table 14.2.7 Proportion of patients having reduction in total IgG (FAS).

Table 14.2.8. Patient survival (FAS)

Table 14.3.1 Overview of AEs (FAS).

Table 14.3.2 Summary of AEs – by SOC and PT (FAS).

Table 14.3.3 Summary of AEs – by causality (FAS).

Table 14.3.4 Summary of AEs – by severity (FAS).

Table 14.3.6 Summary of SAEs (FAS).

Table 14.3.7 Summary of SAEs – by causality (FAS).

Table 14.3.10 Summary of SAEs leading to death (FAS).

Table 14.3.11 Summary of SAEs leading to withdrawal (FAS).

Table 14.4.1 Summary of clinical chemistry variables (U-Albumin, Creatinine, U-Albumin/creatinine ratio) – by time point (FAS).

Table 14.4.2 Anti imlifidase IgG (ADA) (mg/mL) – by time point (FAS)

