9.2 Listings

Listing 16.1.1 Patient disposition, including reason for discontinuation (All screened patients).

Listing 16.1.2 Protocol Deviations (FAS).

Listing 16.1.3 Demography and body measurements (FAS).

Listing 16.1.4 Medical and surgical history (FAS).

Listing 16.1.5 Concomitant medication (FAS).

Listing 16.1.6 Previous transplant kidney history (FAS).

Listing 16.2.1 MFI levels for DSA – by time point (FAS).

Listing 16.2.2 Kidney function (based on S/P-creatinine analysis) (FAS).

Listing 16.2.3 Proportion of patients with absence of graft loss at 1 year, 2 years and 3 years (FAS).

Listing 16.2.4 Proportions of patients with presumed or biopsy proven AMR episodes (FAS).

Listing 16.2.5 Proportion of patients with presumed or biopsy-proven rejection episodes, (other than AMR episodes) (FAS).

Listing 16.2.6 Total IgG – by timepoint (FAS).

Listing 16.2.7 Proportion of patients having reduction in total IgG (FAS).

Listing 16.2.8. Patient survival (FAS).

Listing 16.3.1 AEs (FAS).

Listing 16.3.2 AEs – by SOC and PT (FAS).

Listing 16.3.3 Serious adverse event SAEs (FAS).

Listing 16.4.1 Clinical chemistry variables (U-Albumin, Creatinine, U-Albumin/creatinine ratio) – by time point (FAS).

Listing 16.4.2 Anti imlifidase IgG (ADA) (mg/mL) – by time point (FAS)

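### Non-AMR rejection is analysed as biopsy-proven only, although its endpoint, table and listing count presumed or biopsy-proven episodes

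*SAP*

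**What the plan says.** The endpoint is stated three times with the same scope. The Protocol synopsis has "Proportion of subjects with presumed or biopsy-proven rejection episodes, (other than AMR episodes) classified according to Banff 2017", Protocol 2.2.2 has "Proportion of subjects with presumed or biopsy-proven rejection episodes, (other than AMR episodes", and SAP 1.1.2 has "Proportion of patients with presumed or biopsy-proven rejection episodes, (other than AMR episodes". The planned outputs follow it: "Table 14.2.5 Proportion of patients with presumed or biopsy-proven rejection episodes, (other than AMR episodes) (FAS" in SAP 9.1 and "Listing 16.2.5 Proportion of patients with presumed or biopsy-proven rejection episodes, (other than AMR episodes) (FAS" in SAP 9.2.

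The analysis sections are narrower. Protocol 12.4.4 plans the "proportion of subjects with biopsy-proven rejection episodes, (other than AMR episodes) within 3 years after start of treatment in feeder trial". SAP 4.4.2.4 repeats this with patients in place of subjects: "proportion of patients with biopsy-proven rejection episodes, (other than AMR episodes) within 3 years after start of treatment in feeder trial". In both sections the first half of the sentence keeps presumed episodes for AMR.

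On follow-up, SAP section 6 records that "The study was terminated prematurely in January 2023". The SAP took effect on 12 May 2023. SAP 3.1 and 4.1.1 base all outputs on the FAS and present categorical data as number and percent.

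**The concern.** One secondary endpoint has two definitions. Because AMR keeps the wider definition in the same sentence, the narrower one cannot be read as shorthand. A programmer following 4.4.2.4 would drop patients whose only non-AMR episodes were presumed; one following the table title would count them. Either could claim to comply with the SAP. SAP section 7 plans independent review of the output programs but no double programming, so the choice may go unnoticed. In a descriptive trial of at most 30 patients, the reported proportion is the whole result for this endpoint.

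The smaller matter concerns both rejection proportions. The text of 4.4.2.4 was finalised after the early stop, yet it still describes a 3-year period and has no rule for a patient who was event-free when follow-up ended early.

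**Working it through.** **Definition, place by place (non-AMR rejection)**

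| Place | Episodes counted |
|---|---|
| Protocol synopsis, secondary endpoints | presumed or biopsy-proven |
| Protocol 2.2.2 | presumed or biopsy-proven |
| SAP 1.1.2 | presumed or biopsy-proven |
| SAP Table 14.2.5 (title) | presumed or biopsy-proven |
| SAP Listing 16.2.5 (title) | presumed or biopsy-proven |
| Protocol 12.4.4 (analysis) | biopsy-proven only |
| SAP 4.4.2.4 (analysis) | biopsy-proven only |

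Five places agree with one another. The two that differ are the analysis sections, and the SAP one repeats the protocol one.

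**Weight of one patient.** Protocol 12.6 anticipates 20 imlifidase and 10 plasma exchange patients; SAP 2.2 gives 30 as the maximum. One patient with only presumed non-AMR episodes changes the percentage by 100/n:

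- imlifidase: 100/20 = 5 points
- plasma exchange: 100/10 = 10 points
- total column: 100/30 = 3.3 points

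These are the smallest steps possible, since enrolment can only be lower. With 15 and 7 enrolled, for example, they are 100/15 = 6.7 and 100/7 = 14.3 points. The plan has no figure of its own to reproduce: there is no power calculation, and neither document gives rejection counts.

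**Follow-up.** Protocol 3.4 defines the planned end of trial as last subject last visit, and Protocol 3.2 puts that 3 years (± 4 months) after the last subject's first feeder visit. A premature stop therefore implies that some planned Year 3 follow-up was not completed. SAP 4.4.1 states a censoring rule for graft survival only. SAP 4.1.4 leaves missing data missing in general and does not mention rejection. If event-free patients with short follow-up count as event-free over the whole FAS, the percentage is a count up to termination.

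**Illustration of the follow-up effect (assumed inputs).** Protocol 3.2 implies a first feeder treatment in October 2019, as planned; January 2023 is 39 months later. Assume uniform accrual over A months and a true 3-year risk p = 30%. The share with 36 months of possible follow-up is (39 − 36)/A. The expected crude proportion is the average, over entry times a from 0 to A, of F(min(36, 39 − a)), where F(t) = 1 − (1 − p)^((t/36)^k). Here k = 1 is a constant hazard and k = 0.5 a front-loaded one.

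| A (months) | Share with 36 months | Crude, k = 1 | Crude, k = 0.5 | Shortfall from 30% |
|---|---|---|---|---|
| 6 | 3/6 = 50% | 29.5% | 29.7% | 0.3 to 0.5 points |
| 12 | 3/12 = 25% | 27.6% | 28.8% | 1.2 to 2.4 points |
| 33 (limiting case) | 3/33 = 9% | 19.5% | 23.8% | 6.2 to 10.5 points |

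Accrual length, risk and hazard shape are all assumptions. The spread shows that the documents do not settle the size. With accrual of up to 12 months the shortfall is below the weight of one patient in 20.

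**The case against.** The strongest reply is that this is a descriptive secondary endpoint in at most 30 patients, with no hypothesis test and with all data listed by patient. The table and listing titles already follow the endpoint, and nothing shows that any presumed-only non-AMR episode occurred. All of this stands and limits the weight of the point. It does not remove the contradiction, because the section that defines the analysis says something else.

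A reader might infer that the SAP narrowed the definition without recording it in section 6. The documents do not support that. SAP 4.4.2.4 matches Protocol 12.4.4, so there was no departure from the protocol analysis to record.

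A reader might also infer that the outputs will present truncated counts as 3-year proportions with no sign of incomplete follow-up. That goes too far. The titles of Tables 14.2.4 and 14.2.5 and of their listings carry no time label. The endpoint list says up to 3 years for non-AMR rejection. SAP 4.2 and Table 14.1.1 report completion and withdrawal by arm, and section 6 discloses the termination. What remains is the wording of 4.4.2.4 and the missing classification rule.

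Nor is it right that little is recorded for presumed non-AMR episodes. Protocol 5.1 mentions therapies for recurrent AMR, but Protocol 3.1, 6.1.2, 6.2 (footnote 2) and 7.2.4 collect treatments, creatinine and local DSA results for graft rejection episodes generally.

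**Conclusion.** The definition mismatch is established by the text and needs no assumption: followed literally, SAP 4.4.2.4 reports something other than the stated endpoint and other than the title of the table it feeds. The effect is 5 or 10 points per presumed-only patient at the planned arm sizes, and more with smaller enrolment. The number of such patients is unknown and may be zero. No error rate or power is affected. The correction should be made because it is cheap and settles which number is reported.

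The follow-up point is secondary and is confined to the text of 4.4.2.4. It is tempting to conclude that the proportions understate 3-year incidence by a stated amount, but the documents give neither the last feeder treatment date, nor the number enrolled, nor a rejection rate. The shortfalls shown are illustrative only. They do not justify requiring a time-to-event estimate.

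**What to change.** 1. In SAP 4.4.2.4, define the non-AMR proportion as presumed or biopsy-proven, and show biopsy-proven as a sub-row in Table 14.2.5 so that both readings are visible.
2. Cite the eCRF field or rule that makes an episode presumed; neither document gives one.
3. Note in SAP section 6 that this follows the endpoint and not the wording of Protocol 12.4.4.
4. State in 4.4.2.4, for both rejection proportions, that the crude count over the FAS covers episodes observed up to 3 years, last contact or termination, whichever came first. Show follow-up by arm alongside, for example the numbers followed to Years 1, 2 and 3.

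The cost is a few lines of SAP wording, one entry in section 6, and extra rows in Tables 14.2.4 and 14.2.5. The crude count needs no new data.

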7.2.5 Donor-specific antibody (DSA) levels

Samples for determination of DSA will be analyzed in a single antigen bead assay (SAB-HLA). These assays allow determination of the mean fluorescence intensity (MFI) of antibodies in subject serum reacting to an array of individual HLA immobilized to beads. Analyses of DSA, will be performed centrally at Hansa Biopharma, Lund, Sweden, for samples taken at the visits. The date and actual time of collection of each sample will be recorded in the eCRF.

DSA analysed as standard of care and associated with a graft rejection episode will be recorded in the eCRF. DSAs for each patient will be identified by the respective site.

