4.1.4 Data imputation

In general, missing data will remain as missing and the missing values will not be adjusted. There are some expectations described below.

Adverse events

Missing values will be treated as missing except for causality, toxicity, intensity, seriousness and outcome of an AE, in which case a “worst case” approach will be taken. If causality is missing, it will be set to “related”. If intensity is missing, it will be set to “severe”. If seriousness is missing, it will be considered as a Serious Adverse Event (SAE). If outcome is missing and no date is given for the outcome it will set to “not yet recovered”.

Dates for adverse event and concomitant medical

Missing or partial start dates for adverse events and concomitant medication data will be handled in the following way:

- If the start date is totally missing, the date will still be missing.

- If the start day is partial where only the year are given, then the two cases are considered:
 - If the available partial date (year) is equal to or after the year of treatment start date, then the start date will be imputed as start of the year (1st January YYYY) (if the year is not same as that of the treatment start date) or treatment start date (if the year is same as the treatment start date).
 - For the partial end dates will similar procedure be used as for the start dates. The only difference is the imputation for missing days. Missing days is imputed to the end of the month instead of the start of the month. It will be checked that the imputed end dates fall after the corresponding start dates.

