9.3 Figures

Figure 14.2.1 Individual plots DSA (including sum of DSA) vs time (FAS).

Figure 14.2.2 Mean plots of sum of DSA vs time (FAS).

Figure 14.2.3 Individual Anti-imlifidase IgG (ADA) vs time (FAS).

Figure 14.2.4 Mean Anti-imlifidase IgG (ADA) vs time (FAS).

Figure 14.2.5 Mean Anti-imlifidase IgG (ADA) box plot

10 Change log

Version	Effective date	Reason for revision
1.0	12-May-2023	New document

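### The only group-level DSA curve averages summed MFI over whoever was sampled each year, so after the early stop it mixes change within patients with a change of patients

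*SAP*

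**What the plan says.** SAP 4.4.2.5 plans to summarise, list and plot DSA at Years 1, 2 and 3. Individual plots carry the patient's summed DSA as a separate line. For the group, "Mean plots will display the mean of" that sum. The figure list in SAP 9.3 matches this:

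- "Figure 14.2.1 Individual plots DSA (including sum of DSA) vs time (FAS"), for individuals;
- "Figure 14.2.2 Mean plots of sum of DSA vs time (FAS"), the only group-level DSA figure.

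Three general rules bear on these outputs.

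- SAP 4.1.1 gives n, arithmetic mean, median, SD, minimum and maximum for numerical data, and says that 95% intervals will be presented.
- SAP 4.1.2 defines change from the feeder-trial baseline for relevant endpoints, without naming DSA.
- SAP 4.1.4 says: "In general, missing data will remain as missing and the missing values will not be adjusted".

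SAP section 6 records that "The study was terminated prematurely in January 2023". The SAP is dated 12 May 2023, after that stop. No listed output is a change in DSA from baseline or a summary in the same patients at two visits.

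**The concern.** Protocol 1.1 gives the likely rebound of DSA as the reason for studying long-term benefit, and DSA at Years 1, 2 and 3 is a secondary endpoint. Figure 14.2.2 is where a reader will look for a rebound at group level.

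Summed MFI is positive, depends on how many DSAs a patient has, and is likely to be right-skewed with large differences between patients. The arms hold at most about 20 and 10 patients (Protocol 12.6). In groups of that size one high value moves an arithmetic mean a long way, and so does its absence at a later visit. If the Year 3 point rests on different patients from the Year 1 point, the line can rise or fall although no patient changed, or stay flat or fall while most patients rebound.

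**Working it through.** The documents give no DSA mean, SD or yearly count, so there is no planned figure to reproduce. MFI values, log-SDs and later sample counts below are assumptions.

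**1. What the curve measures.** Let S_ik be patient i's summed DSA at Year k. The plotted point is the mean of S_ik over those sampled at Year k. If everyone sampled at Year 3 was also sampled at Year 1:

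plotted change = [mean of (S_i3 − S_i1) in Year 3 patients] + [mean S_i1 in Year 3 patients − mean S_i1 in all Year 1 patients].

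The first term is change within patients. The second is change of patients, and Figure 14.2.2 cannot separate them.

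**2. Who can reach each visit.** Protocol 3.2 plans the first visit for October 2020, one year after the first feeder treatment, so treatment began about October 2019. Protocol 6.1.2 allows ±4 months at Years 2 and 3. With visits ending in January 2023:

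- Year 3: treated by about January 2020 (36 months), or May 2020 at the edge of the window (32 months). That is the first 3 to 7 months of feeder treatment.
- Year 2: treated by about January 2021 (24 months), or May 2021 (20 months).

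**3. Two worked cases (illustrative MFI).**

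- *Apparent rebound from one patient.* Ten patients at 5,000, one rises to 50,000: (9 × 5,000 + 50,000)/10 = 9,500, or +90%. The geometric mean rises 26% and the median is unchanged. With 20 patients the mean is 7,250, or +45%.
- *Masked rebound.* Nine patients at 4,000 and one at 60,000: mean (36,000 + 60,000)/10 = 9,600. The nine double to 8,000 and the tenth is not sampled: mean 8,000, or −17%. By step 1: +4,000 within patients, and 4,000 − 9,600 = −5,600 from change of patients, total −1,600. With 20 patients the same pattern gives 6,800 to 8,000 (+18%), although every remaining patient doubled.

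**4. How often, with no true change.** Model: log S_ik = b_i + e_ik, with between-patient SD of b 0.8 or 1.2, within-patient SD of e 0.4, and a random subset sampled at Year 3. The table gives the chance that the Year 1 and Year 3 values differ more than 1.5-fold. The arithmetic-mean entries are simulated, and repeat runs move them by up to about one point.

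| Year 1 to Year 3 | Arithmetic mean, log-SD 0.8 | Arithmetic mean, log-SD 1.2 | Same-patient log ratio |
|---|---|---|---|
| 20 to 8 | 22% | 39% | 4% |
| 10 to 4 | 36% | 50% | 15% |

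The last column has a closed form. With m patients at both visits, SE = 0.4 × √(2/m), and ln 1.5 = 0.405. For m = 8: SE 0.200, z = 2.03, two-sided 4%. For m = 4: SE 0.283, z = 1.43, two-sided 15%. This is visit-to-visit noise only.

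**5. Does a ratio to baseline suffice alone?** Let change from baseline differ between patients (log-SD 0.6 to 1.2) but be the same at Years 1 and 3, so that nobody changes between those visits. Chance of a shift over 1.5-fold:

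| Year 1 to Year 3 | Arithmetic mean | Ratio to baseline, all sampled | Same patients at both visits |
|---|---|---|---|
| 20 to 8 | 30–54% | 12–29% | 4% |
| 10 to 4 | 44–62% | 27–46% | 15% |

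The baseline ratio helps, and matching completes the repair. Unpaired geometric means do not: they still shift more than 1.5-fold in 27% of trials (20 to 8, log-SD 1.2).

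**6. When the problem is small.** With constant DSA and 20 falling only to 15, a spurious shift of at least 25% occurs in 0%, 7% and 18% of trials at log-SD 0.6, 1.0 and 1.4.

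**The case against.** The strongest reply is that the mean plot is one display among several. Individual DSA plots, a by-patient MFI listing (16.2.1) and an MFI table by time point (14.2.1) are planned, and the general rules give that table n, median and range. With so few patients, a careful reader could see an outlier or a shrinking group. That stands, and it rules out saying that DSA is shown only as a mean. But none of these outputs is a matched group summary, and none corrects the curve.

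SAP 4.1.2 is already a paired rule, since change is missing if either value is missing, and silence in 4.4.2.5 does not prove that DSA is excluded. That also stands. The gap is that neither the section nor the output list applies the rule to DSA.

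A reader might infer three stronger things that the documents do not support.

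- *That 95% intervals for the DSA means will under-cover.* The SAP names no interval method for them and puts no interval on Figure 14.2.2, so any coverage figure would be conditional on an assumed t-interval.
- *That the set of DSAs being summed drifts between visits.* Protocol 7.2.5 says only that "DSAs for each patient will be identified by the respective site". Nothing says that the list changes.
- *That ADA has the same gap in full.* "Figure 14.2.4 Mean Anti-imlifidase IgG (ADA) vs time (FAS") also averages over changing patients, but ADA has individual and box plots too (Figures 14.2.3 and 14.2.5).

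**Conclusion.** The concern holds for Figure 14.2.2. As specified, it compares different patients at Years 1, 2 and 3 on the question that the protocol gives as its reason for long-term follow-up, and it can show or mask a rebound. It does not hold as a statement that the SAP hides individual DSA data.

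The size is illustrative: a spurious difference over 1.5-fold in roughly 22% to 39% of trials (20 to 8) or 36% to 50% (10 to 4), against 4% and 15% in the same patients. This rests on the lognormal model, the assumed SDs and counts, and random loss. Loss related to graft failure could add bias. The calendar argument assumes that the planned October 2020 first visit took place, that visits ceased in January 2023, and that samples from early end-of-trial visits are not counted as Year 3. *Arithmetic* and *untransformed* are the natural reading of SAP 4.1.1 and 4.4.2.5, not words used about the plot.

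The endpoint is secondary and descriptive, so this should be changed but does not threaten the primary analysis.

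**What to change.** In SAP 4.4.2.5, Table 14.2.1 and Figure 14.2.2:

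1. Apply SAP 4.1.2 to DSA by name, as each patient's log(sum of DSA at Year k / sum at feeder baseline).
2. Report and plot the geometric mean ratio with 95% CI and n, by arm and year.
3. Add the same summary restricted to patients sampled at both visits being compared, because the baseline ratio alone does not remove the effect of changing patients.
4. Print n at every plotted point, and keep the individual plots.
5. For the ADA mean plot, show n and the same-patient subset.

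The cost is SAP wording, one derived variable and one extra summary. It needs no new data collection, since SAP 4.1.2 already relies on feeder baselines. The drawbacks are that patients without a baseline or a later sample drop out of the ratio, matched groups at Year 3 may be very small, and zero values need a floor stated in advance.
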